The occurrence of renal calculi (1.5% to 1.9% incidence) was observed in clinical studies and post-marketing reports of topiramate in adult and pediatric subjects ≥ 2 years of age with epilepsy. The majority of cases did not require surgical intervention. Kidney stones have also been reported in infant subjects during long-term (up to 1 year) topiramate treatment. In an open-label extension study (TOPMAT-PEP-1002_3001 OLE) of 284 pediatric subjects 1 to 24 months old with epilepsy, 7% developed kidney or bladder stones, which were primarily asymptomatic and were assessed systematically by renal ultrasound. Topiramate is not approved for pediatric patients less than 2 years of age.³⁸

The mechanism is believed to be associated with the carbonic anhydrase inhibitory activity of topiramate. Carbonic anhydrase inhibitors (eg, zonisamide, acetazolamide, or dichlorphenamide) can promote stone formation by reducing urinary citrate excretion and by increasing urinary pH.³³

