Only AED monotherapy will be used for both treatment groups. However, subjects will not be discontinued from the study if 1 or more concomitant AEDs are added after initiating treatment with study drug. Data will be collected prior to the use of the concomitant AED(s) for the primary analysis. Data subsequently collected while on the concomitant AED(s) will be analyzed in a secondary analysis for each safety outcome of interest.

All subjects will enter a 30-day posttreatment phase after completing the open-label treatment phase.

The open-label treatment phase has 2 periods, titration and maintenance.

Titration Period

Randomization will take place on Day 1 (Visit 2). The Day 1 visit will serve as the baseline visit. All procedures on Day 1 (except dispensing of study drug) should be completed before randomization.

Study drug will be titrated as tolerated to the maximum recommended dosage for optimal clinical effect over approximately 6 to 8 weeks, based on titration guidelines according to clinical response (see Section 6, Dosage and Administration). For all subjects, at any time, up-titration of open-label study drug may be slowed down if clinically indicated for tolerability, and may be accelerated if clinically indicated for seizure control.

Subjects will return for a clinic visit at Month 1 and Month 2 for dispensing of study medication.

Maintenance Period

Subjects should be maintained on the dosage achieved at the end of the titration period through the remainder of the open-label treatment phase, with the option for dosage adjustment as required for optimal clinical effect. Changes to this schedule will be based on a risk-benefit assessment of the subject's clinical condition by the investigator.

Clinic visits will be scheduled at Months 1, 2, 3, 6, 9, and 12/early withdrawal. Extra visits may be scheduled at the discretion of the investigator. Blood samples for PK evaluations will be taken at Months 1, 3, 6, and 12/early withdrawal.

Posttreatment Phase

[figure not shown]
Subjects will be contacted by telephone 30 days after the last dose of study drug to monitor adverse events and concomitant medications. Subjects who complete the study or discontinue early from the study may, at the discretion of the investigator, either continue on commercially available topiramate or levetiracetam or taper off topiramate or levetiracetam over a period of up to 2 weeks during the posttreatment phase.

Post-Study Follow-up Phase

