8. PRESTUDY AND CONCOMITANT THERAPY

Prestudy AEDs and other medications taken within 2 years prior to the study must be recorded at screening.

Concomitant therapies must be recorded throughout the study beginning with the start of the first dose of study drug. Concomitant therapies should also be recorded beyond 30 days after the last dose of study drug, but only in conjunction with new or worsening adverse events or serious adverse events that meet the criteria outlined in Section [12.3.2](#), Serious Adverse Events.

All therapies (prescription or over-the-counter medications, including vaccines, vitamins, herbal supplements; non-pharmacologic therapies such as electrical stimulation, acupuncture, special diets, exercise regimens) different from the study drug must be recorded in the CRF. Modification of an effective preexisting therapy should not be made for the explicit purpose of entering a subject into the study.

For subjects receiving an AED at baseline, this AED should be tapered down and discontinued during the titration period. Concomitant AEDs at baseline used for any purpose will be withdrawn in one-third decrements during the 6- to 8-week titration period.

Only AED monotherapy will be used for both treatment groups. In the event of insufficient seizure control or intolerability, it should be explored first if a dosage adjustment of the study drug might be useful before adding another AED. However, subjects will not be discontinued from the study if 1 or more concomitant AEDs are added after initiating treatment with study drug. Data will be collected prior to the use of the concomitant AED(s) for the primary analysis. Data subsequently collected while on the concomitant AED(s) will be analyzed in a secondary analysis for each safety outcome of interest.

Other prohibited concomitant medications include:

- Ocular medications, except lubricating eye drops or topical antibiotics
- Furosemide, hydrochlorothiazide, vigabatrin, vitamin B₆ therapy for epilepsy, monoamine oxidase (A or B) inhibitors, or felbamate
- Any other medication that is a potent carbonic anhydrase inhibitor (eg, acetazolamide, furosemide, zonisamide)
- Citrate treatment
- Medications that may affect bone metabolism taken for more than a 10-day treatment course, including intravenous or oral steroids, growth hormone, NSAIDs, antacids, calcium, vitamin D, or multivitamins

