5.6. Prior and Concomitant Medications

Medications administered prior to the first dose of study medication will be considered prior medications. Concomitant medications include those taken on or after first dose date. Incidence of prior and concomitant medications will be summarized by Anatomical Therapeutic Chemical (ATC) code levels 2 and 4, and preferred term. Only prior anti-epileptic drugs (AEDs) will be summarized. Concomitant medications will be listed and summarized separately for AED and non-AED medications. Tables will be sorted by decreasing frequency in incidence (the highest to lowest incidence) first within ATC code level 2, followed by ATC code level 4, and then preferred term. Medications with partial onset date will be handled as follows: a missing day should be set to first of month. If month is missing the missing month should be set to January.

Please see [Appendix 7](#) for the list of AED medications.

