3. If the above doesn't work, then a reduced model with treatment group, age group, visit, treatment-by-visit interaction, and baseline measure will be explored. Age will be collapsed to two categories: 2-9 years of age (pre-pubertal) and 10-15 years of age (pubertal). The unstructured covariance matrix will be explored first and if it doesn't work, then compound symmetric followed by AR1 will be applied.
4. If above doesn't work, then no additional MMRM analysis will be performed. 95% CI for the estimated treatment differences will be provided.

Example of MMRM is as follows:

```
ods output estimates=est;
PROC MIXED data=dat method=REML noclprint=10;
CLASS trt center usubjid age_group visit;
MODEL change=trt base visit center age_group trt*visit base*visit /
solution; repeated visit / type=un subject=usubjid;
lsmeans trt/diff cl;
```

Sensitivity analyses for height z-scores, weight-z-scores and BMD z-scores will be conducted for subset of safety analysis set: for subjects who started taking at least one concomitant AED, data collected after the start of taking AED medication will be excluded from the analysis.

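### The protocol's primary analysis stops at an added AED; the SAP's main analysis does not, and its pre-AED cut covers only three Z-scores and has an unclear trigger

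*SAP*

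**What the plan says.** **Protocol.** The rule stands in the synopsis and in Sections 3.1, 3.2.2 and 8. Study drug is given as monotherapy, but a child who adds an AED stays in the study. For that child, "Data will be collected prior to the use of the concomitant AED(s) for the primary analysis". Then: "Data subsequently collected while on the concomitant AED(s) will be analyzed in a secondary analysis for each safety outcome of interest". Section 3.2.2 gives the reason, which is that any concomitant AED could confound the results. Section 10.1 does not count a child who adds an AED and stays to Month 12 as a completer.

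**SAP.** Section 3.3 uses the safety analysis set for everything except disposition, and Section 3.3.3 defines that set as all randomized and dosed subjects. Neither section cuts data at an added AED. The cut appears in Section 7 and in the summary of SAP Amendment 1: "Sensitivity analyses for height z-scores, weight-z-scores and BMD z-scores will be conducted for subset of safety analysis set". For children who start a concomitant AED, "data collected after the start of taking AED medication will be excluded from the analysis".

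**Trigger.** SAP 5.6 says: "Concomitant medications include those taken on or after first dose date". Protocol Section 8 says: "For subjects receiving an AED at baseline, this AED should be tapered down and discontinued during the titration period". SAP Appendix 7, which identifies the AEDs, lists both study drugs and several benzodiazepines.

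**The concern.** The objectives in both documents compare topiramate monotherapy with levetiracetam monotherapy. All-data results answer a different question: the effect of starting on one drug or the other, whatever is added later. Either question can be defended. However, the protocol chose the first, and the SAP makes the second its main analysis without saying why.

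Add-on treatment could move the results in either direction. Topiramate added in the levetiracetam arm would dilute the contrast. Protocol 16.1 cites publications suggesting that carbamazepine and valproic acid may lower BMD, so adding either could shift bone outcomes in whichever arm it is used more.

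For height, weight and BMD Z-scores a reader will at least see both versions. For stones, BMC, raw height, height velocity and bone age, only the all-data version is planned. The protocol's separate analysis of data collected on the added AED is missing from the SAP altogether.

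**Working it through.** **1. Outcome by outcome.** All of these are key safety endpoints in Protocol 11.4, and the protocol's pre-AED rule makes no exception among them.

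| Outcome | SAP section | Main SAP output | Pre-AED output |
|---|---|---|---|
| Weight Z-score | 7.2 | all data | sensitivity |
| Height Z-score | 7.3 | all data | sensitivity |
| BMD Z-score | 7.4 | all data | sensitivity |
| Kidney stones | 7.1 | all data | none |
| Raw height, height velocity | 7.3 | all data | none |
| BMC | 7.4 | all data | none |
| Bone age | 7.6 | all data | none |

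It is also unclear whether the BMD Z-scores in the sensitivity analysis include the height-adjusted Z-scores and the percentages with a decrease above 0.5, 1.0 and 2.0.

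**2. Is the change explained?** SAP Section 1 says the SAP was modified because of early termination. The Amendment 1 summary lists the AED sensitivity analysis as a major addition. Neither says that the protocol's primary dataset has become a sensitivity dataset, or why.

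**3. The trigger.** Under SAP 5.6, a baseline AED still being tapered after the first dose is concomitant, yet it started before Day 1. If the cut runs from that start date, all of the child's post-baseline data go. If only newly started AEDs count, none go on that account. The SAP wording allows both. It also does not exempt the assigned study drug, or say whether a single rescue dose of a listed benzodiazepine ends a child's data.

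**4. What the cut would cost in precision.** Plan figures first.
- Sample size: 100 / (1 − 0.29) = 140.8, so 141 per arm and 282 in total, as stated.
- Half-width = 1.96 × SD × √(2/n).
- Height: 1.96 × 0.28 × √(2/53) = 0.107 (stated 0.11).
- Weight: 1.96 × 0.43 × √(2/100) = 0.119 (stated 0.12).
- BMD: 1.96 × 0.40 × √(2/100) = 0.111. The stated 0.12 is slightly wider than the formula gives, which does not affect this point.
- Stones: 7/100 against 0/100, with an interval for the difference built from Wilson limits, gives 0.0186 to 0.1375, a width of 0.119 (stated 0.12).

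Now suppose a share f of the evaluable subjects in each arm is lost to the cut. The half-widths grow by 1/√(1 − f), and the stone interval is recomputed at n = 100(1 − f). The documents give no add-on rate, so f is an assumption.

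| f | Height | Weight | BMD | Stone CI width |
|---|---|---|---|---|
| 0% | 0.107 | 0.119 | 0.111 | 0.119 |
| 5% | 0.109 | 0.122 | 0.114 | 0.123 |
| 10% | 0.112 | 0.126 | 0.117 | 0.127 |
| 20% | 0.119 | 0.133 | 0.124 | 0.138 |
| 29% | 0.127 | 0.141 | 0.132 | 0.149 |

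If the planned 100 completers are counted as Section 10.1 defines them, children who add an AED are already outside the 100 and the 0% row applies.

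**The case against.** The best defence is that all-data results preserve the randomized comparison, while a cut at an added AED selects on an event after randomization. Protocol 11.1 also puts every randomized subject in the analysis population. The SAP plans no formal testing, so the label of main or sensitivity changes no formal decision. The three Z-scores are the endpoints SAP Section 1 calls key, so growth and bone mineralization each have a pre-AED result. BMC comes from the same scans as BMD, and height velocity from the same heights.

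Part of this stands. The all-data results are worth keeping, and the gap is smaller than it first appears. But Protocol 11.1 says who is analysed, not which of their visits count. Estimates and intervals still have to match the question asked, and nothing covers stones or bone age.

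Some stronger readings are tempting but not supported:
- **No monotherapy answer at all.** The three Z-scores have one. For the rest, ultrasound findings, bone age and concomitant AEDs are all listed, so a post hoc check is possible. What is missing is a pre-specified summary.
- **Other carbonic anhydrase inhibitors contaminating the levetiracetam arm.** A reader could join Appendix 7, which names zonisamide and acetazolamide, to the protocol's statement that "Carbonic anhydrase inhibitors (eg, zonisamide, acetazolamide, or dichlorphenamide) can promote stone formation". Protocol 4.3 and 8 prohibit both drugs, and Appendix 7 only identifies AEDs. Topiramate is not named in those prohibitions, so it is the example that remains.
- **Every child entering on an AED loses all post-baseline data.** That is one reading of an ambiguous sentence.
- **The planned precision refers to monotherapy data.** The completer definition points that way, but the 29% comes from dropout in an earlier study, and nothing there counts AED add-on.

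**Conclusion.** The protocol and SAP disagree on which data form the primary analysis, and the SAP does not justify its choice. No pre-AED summary is pre-specified for stones, BMC, raw height and height velocity, or bone age. The SAP's move of stones to a secondary objective does not remove the need, because that objective is still worded as a monotherapy comparison. The trigger is loose enough for two programmers to build different datasets.

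The amount of bias in the all-data results cannot be stated, because it depends on an add-on rate, drug mix and timing that the documents do not give. Its direction is also open. What can be bounded is the cost of the cut: at the planned size and an assumed loss of up to 20%, no half-width in the table grows by more than 0.014 and the stone interval widens by about 0.02. SAP Section 1 reports that enrolment was stopped early, so actual intervals would probably be wider with or without the cut. This should be corrected, but it does not invalidate the trial.

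**What to change.** 1. **Reconcile the two documents.** Report pre-AED results as the primary analysis, as the protocol states, with all-data results beside them. Otherwise, state in the SAP that the order has been reversed and why.
2. **In either case, extend the pre-AED analysis** to stones, BMC, height and height velocity, and bone age, and state each denominator. For stones, use subjects with at least one post-baseline ultrasound before the cut. For bone age, note that most children who add an AED drop out, because it is read only at baseline and at Month 12 or early withdrawal. For height velocity, state the shortest interval accepted, since the Appendix 6 formula annualizes whatever interval remains.
3. **Define the analysis trigger** as the first AED newly started after Day 1 other than the assigned study drug. A baseline AED being tapered does not count. State how brief rescue use is handled in the dataset.

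The cost is SAP wording, a wider use of a filter already planned, and some extra tables with their denominator rules. The statistical downside is fewer late observations, possibly unequal follow-up between arms and possible selection after randomization, which is why the all-data results stay.

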7.1. Kidney Stones

Percentage of subjects with kidney stones and other US findings suggestive of stones will be summarized by treatment group.

The renal ultrasound findings will also be presented in a listing.

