11.2. Sample Size Determination

A total of 282 randomized subjects, 141 in each treatment group, will be recruited to the study. The sample size takes into account a 1-year dropout rate of 29%, which is a conservative estimate based on the dropout rates observed in a previous monotherapy study in the 6- to 15-year-old age group, Study TOPMAT-EPMN-106, including a dropout rate of 22% in the study overall (both double-blind and open-label phases) and a dropout rate of 35% for the double-blind phase. The sample size was estimated in order to achieve a sufficient precision for the estimates of the treatment effect on the key endpoints. The precision of the confidence interval (CI) estimates for the key safety parameters are shown below:

- *Annual change in BMD (L1-L4) Z-score:* In the Bone Mineral Density in Childhood Study (BMDCS), mean annual change in BMD (L1-L4) Z-score in 6- to 15-year-old healthy subjects was, as expected, minimal (0.01-0.07).³⁵ The standard deviation (SD) varied from 0.3 to 0.48 across sex and age groups.³⁵ Assuming an SD of 0.4, with 100 completed subjects per group, the 95% CI for the treatment difference will have a precision of 0.12.
- *Annual change in height Z-score in the 2- to 9-year-old age group:* In the monotherapy epilepsy study TOPMAT-EPMN-106, the observed change from baseline in mean height Z-score at 1 year among the 2- to 9-year-old subjects treated with topiramate 400 mg/day was -0.18, with an SD of 0.28.⁴⁰ Assuming that 53% of the subjects will be recruited in the 2- to 9-year-old age group, ie, 53 completed subjects per treatment group, the 95% CI for the treatment difference will have a precision of 0.11.
- *Incidence of kidney stone formation:* In the studies TOPMAT-PEP-3001 and TOPMAT-PEP-1002 in infants (1 month to 2 years of age), a 7% incidence of kidney stones was observed during the 1-year topiramate adjunctive treatment period.^{11,38} A sample size of 100 completed subjects per treatment group will provide a 95% CI (Wilson score CI) for the

treatment difference with a width of 0.12, assuming that the incidence of kidney stone formation is 7% and near zero in the topiramate group and the levetiracetam group, respectively.

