11.4. Safety Analyses

The key safety endpoints will include:

- Percentage of subjects with kidney stones
- Change from baseline in weight Z-score over time
- The following height analyses will be conducted for prepubertal subjects (2 to 9 years of age), subjects 10 to 15 years of age, and subjects 2 to 15 years of age:
 - Height at 1 year postbaseline
 - Height change from baseline over time
 - Height Z-score at 1 year postbaseline
 - Change from baseline in height Z-score over time
 - Height velocity at 1 year postbaseline
 - Height velocity Z-score at 1 year postbaseline
 - Percentage of outlier subjects with height Z-score decrease of >0.5 , >1.0 , and >2.0 over time
- The following BMD and BMC endpoints:

- BMD and BMC over time
 - BMD and BMC change from baseline over time
 - Z-score for BMD and BMC over time
 - Change from baseline in Z-score for BMD and BMC over time
 - Percent change from baseline in BMD and BMC over time
 - Percentage of outlier subjects with BMD Z-score decrease of >0.5 , >1.0 , and >2.0 over time
- Change from baseline in biochemical markers of bone mineralization including: serum levels of alkaline phosphatase, calcium, phosphorus, parathyroid hormone (intact), 25-hydroxy-vitamin D, 1,25-dihydroxy vitamin D, and IGF-1
 - Change from baseline in serum and urine laboratory tests, eg, bicarbonate, ammonia, renal function tests, and LFTs
 - Change from baseline in bone age

Z-scores for the DEXA scans will be calculated locally at baseline and at M12 to determine eligibility for the study and the Post-Study Follow-Up phase, and centrally for all statistical analyses. The Z-score calculation will take the DEXA machine and the subject's age, sex, height, and ethnicity into consideration. The reference databases for calculating the Z-scores are provided in the DEXA Manual for this study.

Longitudinal endpoints will be analyzed using a mixed-model repeated measures (MMRM) analysis. The MMRM model will include treatment group, age group, visit, treatment-by-visit interaction, baseline measure, and baseline-by-visit interaction. An unstructured covariance will be used. Other appropriate covariance structures will be explored as needed. Confidence intervals with 95% confidence for the estimated treatment differences will be provided at each time point as appropriate. For proportion endpoints, 95% confidence intervals will be provided for the treatment difference. Each of the endpoints will also be summarized by age group.

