1. CHANGES IN CONDUCT OF THE STUDY

On 12 December 2018, the independent Data Monitoring Committee (DMC) recommended to stop the TOPMATEPY4067 study because of futility of study enrollment. On 12 August 2019, Janssen has received the US FDA decision as follows:

- Stop enrolling new subjects at all sites and discontinue the study at all the sites that do not have either subject under study treatment or subjects who require a repeat bone mineral density (BMD) measurement 6 months after discontinuing study treatment.
- All sites with any subject on treatment in the study should continue following the subject according to the protocol until treatment has been completed, the subject has discontinued prematurely, or a repeat DEXA scan (which is indicated 6 months after treatment discontinuation) has been completed.

The US FDA decision is based on the slow rate of study enrollment of subjects despite continuous efforts to improve recruitment in the study. The decision is not related to any safety issues.

Interim analyses on the key endpoints (change in BMD z-score at Month 12, change in height z-score at Month 12 and change in weight z-score at Month 12) were conducted on 13 December 2018. This SAP has been modified based on the early termination of the study.

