2.1. Trial Objectives

Primary Objective:

The primary objective is to evaluate the effects of topiramate monotherapy compared with levetiracetam, another standard AED, as monotherapy for new-onset or recent-onset epilepsy on pediatric growth and maturation and bone mineralization, in children 2 to 15 years of age.

Secondary Objective:

To evaluate the effects of topiramate monotherapy compared with levetiracetam, another standard AED, as monotherapy for new-onset or recent-onset epilepsy on kidney stone formation in children 2 to 15 years of age.

Overall safety will be assessed.

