2.3. Statistical Hypotheses for Trial Objectives

The study will test the hypothesis that flexible dosages of topiramate monotherapy have the same effect as flexible dosages of levetiracetam monotherapy on pediatric growth and bone mineralization, in children 2 to 15 years of age with new-onset or recent-onset epilepsy, versus the alternative hypothesis that the effect of topiramate is different from that of levetiracetam.

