7. SAFETY

The safety variables to be summarized include kidney stones, height, weight, BMD and bone mineral content (BMC), biochemical markers of bone mineralization, bone age XR, seizure counts, cognitive, developmental, and behavioral assessments, treatment-emergent AEs, Columbia-Suicide Severity Rating Scale (C-SSRS), cognitive, developmental and behavioral assessments (COGSTATE computerized battery and NEPSY Language scale; Vineland Adaptive Behavioral Scale, Child Behavior Checklist (CBCL)), clinical laboratory tests (hematology, chemistry, urinalysis, and 24-hour urine collection), vital signs and physical exam. Safety variables are to be tabulated by descriptive statistics (n, mean, median, SD, minimum, and maximum; or n and percent). No formal statistical testing is planned.

For markedly abnormal labs and vital signs, age will be calculated at each visit to determine the criteria. Similarly, Vineland, CBCL and Cogstate will be calculated by age at each visit.

Z-scores for weight and height will be calculated using the SAS programs provided by the Centers for Disease Control (CDC) for the calculation of the 2000 CDC growth charts. Z-scores for the BMD and BMC will be provided by the central DEXA reading center (Bioclinica).

Z-scores for the DEXA scans will be calculated locally at baseline only to determine eligibility for the study, and centrally for all statistical analyses. The Z-score calculation will take the DEXA machine and the subject's age, sex, height, and ethnicity into consideration. The reference databases for calculating the Z-scores are provided in the DEXA Manual for this study (please see the imaging charter of attachment 1 for more details).

Longitudinal endpoints will be analyzed using a mixed-model repeated measures (MMRM) analysis. An MMRM analysis is included as sensitivity analysis to explore longitudinal safety data and will be analyzed in the following order.

1. The model includes treatment group, study center, age group (4 age groups), visit, treatment-by-visit interaction, baseline measure, and baseline-by-visit interaction with the unstructured covariance matrix.
2. If this model experiences convergence issues, then the same model with compound symmetric matrix followed by AR1 will be explored instead of unstructured.

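### SAP 7.1, 7.3 and 7.4 drop the 95% confidence interval for the treatment difference that protocol 11.4 promises for proportion endpoints, without saying so or giving a reason

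*SAP*

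**What the plan says.** Protocol 11.4 lists the percentage of subjects with kidney stones, and the percentages whose height or BMD Z-score falls by more than 0.5, 1.0 or 2.0, among its key safety endpoints. It then commits: "For proportion endpoints, 95% confidence intervals will be provided for the treatment difference". The synopsis repeats this. Protocol 11.2 sizes the stone endpoint by precision and names the method: "A sample size of 100 completed subjects per treatment group will provide a 95% CI (Wilson score CI". The stated width is 0.12, assuming 7% on topiramate and close to zero on levetiracetam.

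The SAP's general rule in section 7 is: "Safety variables are to be tabulated by descriptive statistics (n, mean, median, SD, minimum, and maximum; or n and percent". It adds that no formal testing is planned. Section 7.1 reads: "Percentage of subjects with kidney stones and other US findings suggestive of stones will be summarized by treatment group". A listing follows. Sections 7.3 and 7.4 give numbers and percentages of Z-score outliers by visit. Section 7 has one sentence on comparative intervals, "95% CI for the estimated treatment differences will be provided". It closes the last of the numbered MMRM steps, and 7.2 to 7.4 apply MMRM to changes in the continuous measures only.

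SAP 1 explains the general revision: "This SAP has been modified based on the early termination of the study". Stones move from the protocol's primary objective to a secondary one in SAP 2.1, still framed as topiramate compared with levetiracetam "as monotherapy for new-onset or recent-onset epilepsy on kidney stone formation in children 2 to 15 years of age". They leave the hypothesis in SAP 2.3, which now covers "levetiracetam monotherapy on pediatric growth and bone mineralization, in children 2 to 15 years of age". Their precision statement is missing from SAP 2.4.

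**The concern.** A reporting team that follows the SAP will print two percentages side by side for each of these endpoints, with no estimate of the difference and no measure of its uncertainty. That is less than the protocol promised for an endpoint in its primary objective, and the SAP still sets a comparative objective for it. The outlier proportions for height and BMD belong to objectives that remain primary in the SAP, and they lose the interval too.

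Bare percentages are most likely to mislead when arms are small and one arm has few or no events. The protocol expects the second condition for stones, and early termination makes the first more likely. A reader can rebuild an interval from the counts, but has to choose the method after seeing the data, because the SAP names none.

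**Working it through.** **1. Does any SAP rule restore the interval?** No. Section 3 asks for frequencies and percentages for categorical endpoints. Section 7 asks for n and percent. The only sentence on comparative intervals belongs to the MMRM steps, which do not cover proportions. Sections 7.1, 7.3 and 7.4 add none.

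**2. Reproduce the protocol's figure.** Inputs from protocol 11.2: n = 100 per arm, p1 = 0.07, p2 close to zero (taken as 0), 95%, Wilson score. With Wilson limits (l, u) for each arm, the Newcombe hybrid interval for d = p1 - p2 is

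- lower: d - sqrt[(p1 - l1)² + (u2 - p2)²]
- upper: d + sqrt[(u1 - p1)² + (p2 - l2)²]

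Wilson limits are 0.0343 to 0.1375 for 7/100 and 0 to 0.0370 for 0/100.

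- lower: 0.07 - sqrt(0.0357² + 0.0370²) = 0.07 - 0.0514 = 0.0186
- upper: 0.07 + (0.1375 - 0.07) = 0.1375
- width: 0.119, which rounds to the stated 0.12

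So the protocol's precision claim matches this method. A Wald interval on the same counts is 0.07 ± 1.96 × sqrt(0.07 × 0.93/100) = 0.020 to 0.120, width 0.100, which does not match.

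**3. Vary the arm size.** SAP 1 says enrolment stopped early, and the documents do not give the achieved numbers. The arm sizes below 100 are assumptions. Events are the whole number nearest 7% of n, rounding 3.5 up, against none on levetiracetam. Intervals are in percentage points.

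| Per arm | Events | Newcombe-Wilson | Wald |
|---|---|---|---|
| 100 (planned completers) | 7 v 0 | 1.9 to 13.7 | 2.0 to 12.0 |
| 75 (assumed) | 5 v 0 | 0.5 to 14.7 | 1.0 to 12.3 |
| 50 (assumed) | 4 v 0 | -0.6 to 18.8 | 0.5 to 15.5 |
| 30 (assumed) | 2 v 0 | -5.7 to 21.3 | -2.3 to 15.6 |

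Check of the 50-per-arm row. Newcombe lower: 0.08 - sqrt(0.04845² + 0.07135²) = 0.08 - 0.0862 = -0.006. Wald lower: 0.08 - 1.96 × sqrt(0.08 × 0.92/50) = 0.08 - 0.0752 = 0.005.

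**4. Count the intervals the fix adds.** Height outliers: 3 thresholds × 5 post-baseline windows = 15. BMD outliers without height adjustment: 2 sites × 3 thresholds × 2 windows = 12. Together that is 27. The height-adjusted BMD outliers would add another 12, making 39. At Month 12 only, the unadjusted set is 3 + 6 = 9. These counts are before any age grouping.

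**The case against.** The best defence is that the SAP was deliberately reduced after early termination. Its changes to stones fit together: a lower-ranked objective, no hypothesis, no precision statement, no formal testing. That explains why stones might receive less analysis. It does not explain the missing interval. An interval is estimation rather than testing, and the SAP keeps intervals for MMRM differences in the same section. It does not explain the outlier proportions either, because growth and bone mineralization stayed primary. The SAP never identifies the omission as a change.

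A second defence is that the protocol's commitment was not expressly withdrawn, and that at the planned size the method hardly matters. Both statements are correct. At 100 per arm the lower limits nearly coincide (1.9 and 2.0), both intervals exclude zero, and the upper limits differ by about 1.7 points. The method becomes decisive only at smaller arm sizes, and those are assumed here.

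A reader might also infer that the SAP leaves unscanned children and repeat scans undefined, so that stones could be lost from the count. The documents do not support that. SAP 3 sets a default denominator and 3.3.3 the safety set. SAP 3.1 gives renal ultrasound its own windows and a nearest-to-target rule. A positive scan could drop out of the table only if 7.1 were read per visit, and 7.1, unlike 7.2 to 7.4, does not say by visit. Even then the scan would be listed, and a stone reported as an adverse event would appear under SAP 7.9. Two clarifications remain useful: that a stone on any post-baseline scan counts, and how many children had none, because the default denominator counts them as stone-free. Protocol 10.2 asks for end-of-study assessments at early discontinuation, which should keep that number down.

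**Conclusion.** The point stands as an undocumented departure from protocol 11.4. The comparative interval is missing for kidney stones and for the height and BMD Z-score outlier proportions. It should be fixed, although readers can rebuild intervals from the printed counts.

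The size depends on arm sizes that the documents do not give. At the planning figures the omitted stone interval is 1.9 to 13.7 points. Over assumed arms of 75 down to 30 it runs from 0.5 to 14.7 through to -5.7 to 21.3. At an assumed 50 per arm, Newcombe-Wilson includes zero and Wald does not. These figures assume about 7% against none, as the protocol did.

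Two stronger conclusions are not supported: that the choice of method would change the reading at the planned size, and that the interval was removed because of anything seen in the stone data. SAP 1 attributes early termination to slow enrolment and says that it was not related to safety.

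**What to change.** In SAP 7.1, report the difference in stone percentage (topiramate minus levetiracetam) with a Newcombe-Wilson 95% interval. Add the same interval to the height and BMD Z-score outlier proportions listed in protocol 11.4. The height-adjusted BMD outliers are a SAP addition, so intervals there are optional. If the sponsor prefers to omit the intervals, state this as a change from protocol 11.4 and give the reason.

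As a minor clarification in 7.1, state that a stone on any post-baseline, centrally read ultrasound counts, and report the number of children per arm with no post-baseline scan.

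Cost: SAP wording and extra columns, with no new data. One interval is needed for stones. Sections 7.3 and 7.4 need about 27 if done at every visit and threshold (39 with the height-adjusted outliers), or 9 if limited to Month 12 and the unadjusted outliers, before any age grouping. The intervals will be visibly wide, as the data warrant.
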